#### **4.3 Exploratory Objectives**

- To evaluate if B244 administration on the skin twice daily for 28 days will affect the levels of inflammatory biomarkers. To explore microbial content, microbiota composition, and B244 presence/absence at baseline and Day 28.
- To evaluate the difference between daytime and nighttime ambulatory blood pressure
- To explore and compare the blood pressure change in different ethnic groups, including African American, Caucasian, Asian and Hispanic.

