1.1.2.3. Exploratory Objectives

- To evaluate if B244 administration on the skin twice daily for 28 days will affect the levels of inflammatory biomarkers. To explore microbial content, microbiota composition, and B244 presence/absence at baseline and Day 28.
- To evaluate the difference between daytime and nighttime ambulatory blood pressure (ABP).

- To explore and compare the blood pressure change in different ethnic groups, including African-American, Caucasian, Asian, and Hispanic.

This statistical analysis plan (SAP) is designed to outline the methods to be used in the analysis of study data in order to answer the study objective(s). Populations for analysis, data handling rules, statistical methods, and formats for data presentation are provided. The statistical analyses and summary tabulations described in this SAP will provide the basis for the results sections of the clinical study report (CSR) for this trial.

This SAP will also outline any differences in the currently planned analytical objectives relative to those planned in the study protocol.

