4.3.3. Ambulatory Blood Pressure

The analysis of ABP will be modeled in 3 ways. The first will compare the change in average daytime (8 AM to 4 PM) values of diastolic and systolic blood pressure at baseline to the average values post-baseline using an ANCOVA model with stratification and treatment included in the model. Means and LS means will be reported. All analyses will be performed using the ABPM population.

In addition to the results of the model, mean hourly results, daytime(8 AM to 4 PM), nighttime (10 PM to 6 AM), and 24-hour results will be summarized by treatment group.

This ANCOVA model will also be performed separately for the pre-hypertensive and Stage 1 subjects.

The second method will use piecewise linear functions (linear splines) in which linear slopes of each subject's values over time at baseline and post-baseline periods are calculated. The first "knot" will be placed at the time of treatment and additional knots will be evaluated graphically using lowess smoothing curve graph to determine a second inflection point of non-linearity. By calculating the coefficient of each spline, the rate of change in ABP can be calculated and compared between treatment groups.

ABP will also be analyzed by Dippers and Non-Dippers based on the American Heart Association classification using systolic blood pressure. Dippers and Non-Dippers are defined as follows:

Dipper: 10% decrease in nighttime SBP versus daytime SBP
Non-Dipper: <10% decrease in nighttime ambulatory SBP versus daytime ambulatory SBP.

The shift in dipping classification from baseline to day 28 will be tabulated.

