	Mean (SD)	xx.x (xx.xx)	xx.x (xx.xx)	xx.x (xx.xx)	xx.x (xx.xx)	xx.x (xx.xx)	xx.x (xx.xx)
	Median	xx.x	xx.x	xx.x	xx.x	xx.x	xx.x
	Min, Max	xx, xx	xx, xx	xx, xx	xx, xx	xx, xx	xx, xx

Source: [Listing 16.2.6.1](#)

PROGRAM NAME: XXX

DATE: HH:MM/DDMMYYYY

PROGRAMMING NOTE: Continue for Diastolic Blood Pressure. If the subject has results for more than 24 hours in a visit, only the first time point per hour will be included in the analysis.

Repeat for:

Table 14.2.4B Mixed Model Analysis of Change from Baseline in Daytime Ambulatory Blood Pressure by Hypertension (ABP Population)

Table 14.2.4C Mixed Model Analysis of Change from Baseline in Daytime Ambulatory Blood Pressure by Age Group (ABP Population)

PROGRAMMING NOTE: Add column for each subgroup as applicable per table title.

Table 14.2.5

Change in Proportion of Dippers and Nondippers from Baseline to Day 28 Visit (ABP Population)

Treatment	Baseline	Day 28		Total
		Dipper	Nondipper	
4 Sprays (N=xx)	Dipper	xx (xx.x)	xx (xx.x)	xx (xx.x)
	Non-Dipper	xx (xx.x)	xx (xx.x)	xx (xx.x)
	Total	xx (xx.x)	xx (xx.x)	xx (xx.x)
8 Sprays (N=xx)	Dipper	xx (xx.x)	xx (xx.x)	xx (xx.x)
	Non Dipper	xx (xx.x)	xx (xx.x)	xx (xx.x)
	Total	xx (xx.x)	xx (xx.x)	xx (xx.x)
Placebo (N=x)	Dipper	xx (xx.x)	xx (xx.x)	xx (xx.x)
	Nonipper	xx (xx.x)	xx (xx.x)	xx (xx.x)
	Total	xx (xx.x)	xx (xx.x)	xx (xx.x)

Dipper: 10% decrease in daytime ambulatory systolic blood pressure (SBP) versus the daytime ambulatory SBP.

Nondipper: <10% decrease in nighttime ambulatory SBP versus daytime ambulatory SBP.

Note: Percentages are based on the number of subjects in each treatment group. Subjects in the ABP who are missing any component necessary to calculate dipping are excluded from this table.

Source: [Listing 16.2.6.1](#)

PROGRAM NAME: XXXXXXXXXXXXXXXXXXXXXXXXXXXXXXXXXXXXXXX

DATE: HH:MM/DDMMYYYY

Table 14.3.1.1

Overall Summary of Treatment-Emergent Adverse Events (Safety Population)

Statistic	B244				Placebo (N=xx)	Overall (N=xx)
	4 Sprays (N=xx)	8 Sprays (N=xx)	All B244 (N=xx)			
Subjects with at Least 1 Treatment-Emergent Adverse Event (TEAE)	n (%)	xx (xxx.x)	xx (xxx.x)	xx (xxx.x)	xx (xxx.x)	xx (xxx.x)
Subjects with at Least 1 Treatment-Related TEAE	n (%)	xx (xxx.x)	xx (xxx.x)	xx (xxx.x)	xx (xxx.x)	xx (xxx.x)
Subjects with at Least 1 Grade 3 or 4 TEAE	n (%)	xx (xx.x)	xx (xx.x)	xx (xx.x)	xx (xx.x)	xx (xx.x)
Subjects with at Least 1 Treatment-Related Grade 3 or 4 TEAE	n (%)	xx (xx.x)	xx (xx.x)	xx (xx.x)	xx (xx.x)	xx (xx.x)

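### The exploratory day-night ambulatory blood pressure objective has no planned B244-versus-placebo estimate with a confidence interval; its only within-subject output is a descriptive shift table cut at a 10% fall

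*SAP*

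**What the plan says.** The objective is worded "To evaluate the difference between daytime and nighttime ambulatory blood pressure" (Protocol 4.3; repeated in SAP 1.1.2.3). It is exploratory and, unlike the secondary objectives, does not mention a comparison with vehicle.

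SAP 4.3.3 handles ambulatory pressure as follows:

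- **ANCOVA, daytime only.** "The first will compare the change in average daytime (8 AM to 4 PM) values of diastolic and systolic blood pressure at baseline", set against the post-baseline averages, with strata and treatment in the model.
- **Summaries.** Hourly and daytime values, and "nighttime (10 PM to 6 AM), and 24-hour results will be summarized by treatment group". Table 14.2.3A gives actual values and changes for each period separately, and SAP 4.3.4 graphs them.
- **Linear splines.** Slopes over time are compared between groups.
- **Dipping.** The class is set by the nocturnal fall in systolic pressure: "Non-Dipper: <10% decrease in nighttime ambulatory SBP versus daytime ambulatory SBP". Then: "The shift in dipping classification from baseline to day 28 will be tabulated".

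The Table 14.2.5 shell cross-classifies baseline and Day 28 class for 4 sprays, 8 sprays and placebo. Its note says "Percentages are based on the number of subjects in each treatment group". It has no row for all B244, for a difference, for a CI or for a p-value. Its footnote reads "Dipper: 10% decrease in daytime ambulatory systolic blood pressure (SBP) versus the daytime ambulatory SBP".

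Protocol 15.3.8 says the in-clinic method, which yields differences in LS means with 95% CIs, is also to be used for the ambulatory assessments. SAP section 5 records no departure from this.

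**The concern.** The quantity named in the objective is continuous and belongs to the subject: how far pressure falls from day to night. The SAP derives both components for every subject in the ambulatory population but never defines their difference or ratio as an outcome. Where it does combine them, it keeps only which side of 10% the subject falls on.

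Two things are lost. A subject whose dip moves from 2% to 9% is recorded as unchanged, while one who moves from 9.5% to 10.5% is recorded as a shift. And in a vehicle-controlled trial the useful exploratory result is an estimated difference between arms with its uncertainty, which no planned output supplies for the dip.

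Separately, a dipper footnote that compares daytime with daytime pressure describes a quantity that is always zero, so the class cannot be programmed from the shell as written.

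**Working it through.** **1. The plan's own figure.** No figure is stated for this objective. The only power statement (SAP 3.1) concerns in-clinic systolic pressure: 52 per arm, difference 5.8, SD 10.5, two-sided 0.05. Then 5.8 / (10.5 × √(2/52)) = 2.817, and Φ(2.817 − 1.960) = 80.4% (79.7% by noncentral t), against 80% stated. It reproduces, but says nothing about the dip.

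**2. Which outputs contrast night with day?**

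| Output | Night against day within subject? | Between-arm estimate with CI for that contrast? |
|---|---|---|
| ANCOVA of daytime means (SAP 4.3.3) | No | No |
| Splines (SAP 4.3.3) | No, slopes over time | No |
| Table 14.2.3A and SAP 4.3.4 graphs | No, each period separately | No |
| Dipping status as optional subgroup (SAP 3.8) | Yes, but only to define subgroups | No |
| Table 14.2.5 | Yes, as two classes | No |

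**3. Can the missing interval be recovered from the tables?** Let ΔN and ΔD be a subject's changes in night and day means. Subtracting the tabulated means gives an arm-level point estimate in mmHg. Its variance is Var(ΔN) + Var(ΔD) − 2Cov(ΔN, ΔD). Table 14.2.3A supplies the two variances through the SDs of change, but no shell supplies the covariance.

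**4. What the cut costs.** For a normal measure with a small shift, the relative efficiency of a binary cut is φ(c)² / [p(1 − p)], where p is the share on one side and c = Φ⁻¹(p). The documents do not give p, so a range is shown. The last column takes an effect with 80% power on the continuous scale at 52 per arm, (1.960 + 0.842) × √(2/52) = 0.549 SD, and gives its power as a two-proportion comparison.

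| p (assumed) | Relative efficiency | Equivalent n of 104 | Proportions compared | Power |
|---|---|---|---|---|
| 0.50 | 0.637 | 66 | 0.500 vs 0.709 | 59% |
| 0.40 | 0.622 | 65 | 0.400 vs 0.616 | 60% |
| 0.30 | 0.576 | 60 | 0.300 vs 0.510 | 59% |
| 0.20 | 0.490 | 51 | 0.200 vs 0.385 | 55% |

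**5. Illustrative simulation.** All inputs are assumed: 50 per arm, mean dip 10%, SD 6 points, true effect 3 points, baseline-to-Day 28 correlation r of 0.3, 0.5 or 0.6, and 3,000 trials per setting.

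- ANCOVA of the continuous dip: 74%, 82% and 87% power. Closed form: 0.5 / √(1 − r²) × √25 − 1.960 gives 74.6%, 82.3% and 87.8% by normal approximation.
- Day 28 dipper proportions: 50%, 52% and 52%.
- Change in dipper status: 33%, 36% and 42%.

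The ANCOVA figures include a gain from baseline adjustment. An unadjusted t-test on the continuous dip, with d = 3/6 = 0.5, has about 70% power, so 4 to 17 points of the ANCOVA result (74 − 70 to 87 − 70) come from adjustment. Like for like, both unadjusted at Day 28, the cut costs about 18 to 20 points (70 − 52 to 70 − 50).

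**6. Chance switching.** With no effect and the mean exactly at the cut, the probability of changing class is ½ − arcsin(r)/π = 40.3%, 33.3% and 29.5% for the three correlations. It is lower if the mean lies away from 10%.

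**The case against.** The strongest reply is that a descriptive table suits a descriptive aim. The objective is exploratory and not worded against vehicle, no dipping or day-night endpoint appears in either document's endpoint lists, and SAP 3.2 confines formal testing to primary and secondary endpoints. That stands, so the absence of a test is not a fault. What remains is the missing estimate and interval, which need no claim of significance and agree with Protocol 15.3.8.

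A reader might infer that the trial cannot say whether B244 changes the day-night difference. The documents do not support that. Continuous day and night means are tabulated and graphed by arm, a point difference can be had by subtraction, and subject-level hourly averages are listed (Listing 16.2.6.3). The plan lacks a stated contrast and its CI; it does not lack the data.

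A reader might also infer that the shifts mostly show misclassification. No share can be computed from the documents. The switching rates in step 6 depend on a mean placed at the cut, where chance switching is greatest. Table 14.2.5 also has a randomised placebo group, and chance switching and regression to the mean act on all arms.

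Finally, the simulated powers should not be read as a shortfall in the SAP. It plans neither binary test and sets no power target for this objective.

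The footnote is a separate slip: SAP 4.3.3 and the next line of the same shell state the night-versus-day comparison correctly.

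**Conclusion.** The point holds as a minor, inexpensive improvement. No planned output gives a B244-versus-placebo estimate with a CI for the day-night difference, and the only within-subject contrast is cut at 10% and tabulated. That conclusion rests on the text alone.

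The size of the loss rests on assumptions. About 36% to 51% of the information goes if the dip is roughly normal, treatment shifts it, and 20% to 50% of subjects lie on one side of the cut. The simulation is illustration only, under an assumed mean, SD, effect and correlation. The point does not bear on the primary or secondary conclusions.

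The Table 14.2.5 dipper footnote is wrong as written and contradicts SAP 4.3.3.

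**What to change.** Add to SAP 4.3.3, labelled exploratory and using the ambulatory population, an ANCOVA of the Day 28 systolic dip:

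- **Main measure:** percent dip, 100 × (daytime mean − nighttime mean) / daytime mean.
- **Supportive measure:** daytime mean − nighttime mean, in mmHg.
- **Model terms:** the baseline value of the same measure, spray number, hypertension status and treatment.
- **Report:** B244 minus placebo with a 95% CI.

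Keep Table 14.2.5 as description, and correct its dipper footnote to nighttime versus daytime systolic pressure. While the shell is open, check its source line: it cites Listing 16.2.6.1, whose shell holds the seated readings, while the ambulatory data are in Listings 16.2.6.2 and 16.2.6.3.

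The cost is one or two models and one small table on variables already derived, with no new data. The downside is one or two further exploratory estimates in a plan that makes no multiplicity adjustment (SAP 3.7), which the label should make clear.

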4.3.4. Graphical Analysis of Ambulatory Blood Pressure

Mean blood pressure (\pm SEM) at each hour, daytime, nighttime, and 24-hours at baseline and Day 28 will be graphed with separate lines for each treatment group. Least squares means will be graphed in similar fashion.

4.3.5. Exploratory Analyses

The influence of baseline factors such as race may be included in the models described in [Section 4.3.1](#) if sufficient data are available for secondary analyses.

4.4. Safety Analyses

Safety analyses will be conducted using the Safety population.

4.4.1. Study Drug Exposure

The cumulative amount of study drug exposure will be estimated by calculating the difference between the weight of the 4 bottles of drug at the time the drug was dispensed and the weight of the 4 bottles at the last visit. The amount of product used per day will be estimated by dividing the change by the number of days the subject was on treatment. These weights will be compared to the weight of the product that would be used if the subject was compliant with the protocol and used the spray 4 or 8 times per day for 28 days.

Percent compliance will be summarized for each subject from date of first dose through the treatment period based on the net weight of the product administered. Net weight is calculated as the weight collected at Day 29 (or Day 28, if the subject stopped using the study drug at the visit prior to ABPM placement) minus the weight at Day 1. Based on information provided by AOBiome, the expected amount of study drug used per week is approximately 7.91 g/week for 4 sprays/application and 15.82 g/week for 8 sprays/application.

$$= \frac{(\text{Day 29 weight} - \text{Day 1 weight})}{28} \times 100$$

The number of days the subject administered study drug, the amount of product used, and the percent compliance will be summarized by treatment group and presented in a by-subject data listing. The subject listing will also include by-visit IP weights. Percent compliance will be calculated only for subjects who returned the study drug at Day 28 or Day 29. In the listing, subjects who withdrew from the study early will be flagged.

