### **9 STUDY TREATMENT**

#### **9.1 Investigational Product**

Under normal conditions of handling and administration, IP is not expected to pose significant safety risks to site staff. A Material Safety Data Sheet describing the occupational hazards and recommended handling precautions will be provided to site staff if required by local laws or will otherwise be available from the Sponsor upon request.

Investigational product must be stored in a secure area under the appropriate physical conditions for the product. Access to and administration of the IP will be limited to the Investigator and authorized site staff. Investigational product must be dispensed or administered only to participants enrolled in the study and in accordance with the protocol.

The Investigator is responsible for study treatment accountability, reconciliation, and record maintenance. The Investigator or designated site personnel must maintain study treatment accountability records throughout the course of the study. The responsible person(s) will document the amount of study treatment received from and returned to the sponsor and the amount administered to participants. The required accountability unit for this study will be the bottle. Discrepancies are to be reconciled or resolved.

Product name:	B244, 30ml/bottle	Vehicle, 30ml/bottle
Dosage form:	B244 suspension	Vehicle solution
Unit dose strength:	8x10  cfu/ml	50nM Na 2 HPO 4 -2mM MgCl 2 (pH 7.6)
Route/administration/duration:	Topical application BID for 4 weeks	Topical application BID for 4 weeks
Dosing instruction:	Face: 4 pumps total of spray to saturate the entire face.  Face and Torso: 8 pumps total - 4 pumps of spray to saturate the entire face and 4 pumps to the torso  Applications should occur in the morning and at night for 4 weeks.	Face: 4 pumps total of spray to saturate the entire face.  Face and Torso: 8 pumps total - 4 pumps of spray to saturate the entire face and 4 pumps to the torso  Applications should occur in the morning and at night for 4 weeks.
Physical description:	Odorless, cloudy, light pink suspension	Odorless, clear, and colorless suspension
Manufacturer/source of procurement:	AOBiome, LLC	AOBiome, LLC

The contents of the label will be in accordance with all applicable regulatory requirements. B244 and matching vehicle will be packaged in identical 30 ml white metered bottles.

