## **9.7 Treatment Application**

Subjects will receive a kit consisting of three 30 ml bottles at the Baseline visit for application. Subjects will be instructed in the use of the spray bottle and asked to self-administer the Investigational Product as follows:

- Face: 4 pumps of Investigational Product must be applied twice-a-day to the entire face for 28 days. Subject should saturate the application area well.
- Face and torso: 4 pumps of Investigational Product must be applied twice-a-day to the entire face and 4 pumps of drug must be applied to the torso for 28 days. Subject should saturate the application area well.
- Subjects may not wash the application site after applying the IP
- Subjects will be asked to let the product air dry.
- The spray bottles must be stored in the refrigerator. DO NOT FREEZE.

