## **9.15 Handling of Investigational Product**

Subjects will receive a kit containing three 30 ml white bottles. Each bottle will be used for 10 days and brought to the weekly study appointment. Subjects will be asked to refrigerate bottles that are not in use. The bottle which is being used for treatment at a given week may be placed on the counter to be used during the treatment period.

Subjects will be asked not to subject the treatment kit to conditions which are unnatural or harmful to the product, such as excessive heat (temperatures over 77°F (25°C) and freezing temperatures (at 0°C). Subjects may travel with their study medication but should not leave it in

the hot car, outside in the cold temperatures etc. Subjects will also be asked not to tamper or cause damage to IP.

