1.2. Study Design

1.2.1. Synopsis of Study Design

This is a prospective, vehicle controlled, double blinded, multicenter, randomized Phase II trial, comparing the effect of twice daily B244 application for 4 weeks versus vehicle application on blood pressure and inflammatory biomarkers.

Patients who have clinically confirmed diagnosis of systolic pre-hypertension and Stage 1 systolic hypertension are eligible for enrollment. Patients must be in general good health as determined by a thorough medical analysis.

It is estimated that 116 participants will be consented in order to provide 104 completed participants for randomization, treatment, and inclusion in the primary analysis.

After screening and recruitment, participants will be randomized to active or vehicle B244 application for 28 days. Subjects will apply investigational product (IP) twice-a-day as follows:

- Study Arm 1: 4 pumps to the face
- Study Arm 2: 4 pumps to the face and 4 pumps to the torso

Clinical assessments of response to treatment will be made at Study Day 1 (baseline) and Study Days 7, 14, 21, 28 and 42.

[figure not shown]
Safety evaluations will consist of review of participant's medical history at screening and ongoing assessment of adverse events (AEs) reported throughout the study duration.

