	Mean (SD)	xx.x (xx.xx)	xx.x (xx.xx)	xx.x (xx.xx)	xx.x (xx.xx)	xx.x (xx.xx)
	Median	xx.x	xx.x	xx.x	xx.x	xx.x
	Min, Max	xx, xx	xx, xx	xx, xx	xx, xx	xx, xx
Percent Compliance [3]	n	xx	xx	xx	xx	xx
	Mean (SD)	xx.x (xx.xx)	xx.x (xx.xx)	xx.x (xx.xx)	xx.x (xx.xx)	xx.x (xx.xx)
	Median	xx.x	xx.x	xx.x	xx.x	xx.x
	Min, Max	xx, xx	xx, xx	xx, xx	xx, xx	xx, xx

[1] Cumulative study drug exposure = weight of the 3 drug bottles at last visit - weight of the 4 drug bottles at first dispense.

[2] Amount of product used per day = change / number of days the subject was on treatment.

[3] Percent compliance = (Net weight of study drug) / (Expected net weight for 28 days of use) × 100.

Source: [Listing 16.2.5.1](#), [Listing 16.2.5.2](#)

PROGRAM NAME: XXXXXXXXXXXXXXXXXXXXXXXXXXXXXXXXXXXXXXX

DATE: HH:MM/DDMMYYYY

Repeat for:

Table 14.1.4.1B Summary of Drug Exposure (PP Population)

Table 14.2.1A

Summary of Values and Change from Baseline for Systolic and Diastolic Blood Pressure - Mixed Model Analysis (ITT Population)

Parameter: Systolic Blood Pressure

Visit	Actual/ Change	Statistic	B244			
			4 Sprays (N=xx)	8 Sprays (N=xx)	All B244 (N=xx)	Placebo (N=xx)
Baseline	Actual	n	xx	xx	xx	xx
		Mean (SD)	xx.x (xx.xx)	xx.x (xx.xx)	xx.x (xx.xx)	xx.x (xx.xx)
		Median	xx.x	xx.x	xx.x	xx.x
		Min, Max	xx, xx	xx, xx	xx, xx	xx, xx
Day 7	Actual	n	xx	xx	xx	xx
		Mean (SD)	xx.x (xx.xx)	xx.x (xx.xx)	xx.x (xx.xx)	xx.x (xx.xx)
		Median	xx.x	xx.x	xx.x	xx.x
		Min, Max	xx, xx	xx, xx	xx, xx	xx, xx
	Change	n	xx	xx	xx	xx
		Mean (SD)	xx.x (xx.xx)	xx.x (xx.xx)	xx.x (xx.xx)	xx.x (xx.xx)
		Median	xx.x	xx.x	xx.x	xx.x
		Min, Max	xx, xx	xx, xx	xx, xx	xx, xx
		LS MEAN (SEM)	xx.x (xx.xx)	xx.x (xx.xx)	xx.x (xx.xx)	xx.x (xx.xx)
		95% CI	xx, xx	xx, xx	xx, xx	xx, xx
		LS MEAN Difference B244 - Placebo (SEM)	xx.x (xx.xx)	xx.x (xx.xx)	xx.x (xx.xx)	xx.x (xx.xx)
		95% CI	xx, xx	xx, xx	xx, xx	xx, xx
		P-value [1] (vs Placebo)	0.xx	0.xx	0.xx	0.xx
		P-value [1] (vs 8 Sprays)	0.xx			
Day 14		<as above in Day 7>				
Day 21		<as above>				
Day 28		<as above>				
Day 42		<repeat Actual and Change parameters only>				

Note: Day 42 is not included in model. In the mixed-effect model repeated measures (MMRM) model, the outcome variable is change from baseline in NIS-W. The model includes baseline blood pressure as covariate and fixed effect terms including treatment group, visit, treatment-by-visit interaction and hypertension status.

[1] P-value is derived from the contrast testing at each visit using the MMRM model.

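### SAP 4.4.1 describes compliant use as 4 or 8 sprays per day, half the twice-daily schedule in both documents and at odds with the SAP's own g/week figures

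*SAP*

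**What the plan says.** SAP 1.2.1 sets the frequency: "Subjects will apply investigational product (IP) twice-a-day as follows", followed by 4 pumps to the face, or 4 to the face and 4 to the torso. The protocol agrees. Section 9.7 states "Face: 4 pumps of Investigational Product must be applied twice-a-day to the entire face for 28 days". Section 9.1 gives the larger regimen as "Face and Torso: 8 pumps total - 4 pumps of spray to saturate the entire face and 4 pumps to the torso" and adds "Applications should occur in the morning and at night for 4 weeks".

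SAP 4.4.1 then refers to expected use in three ways:

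- The first paragraph compares cumulative and daily weights with those of a protocol-compliant subject who "used the spray 4 or 8 times per day for 28 days".
- The second paragraph bases percent compliance on net weight and gives expected use as "approximately 7.91 g/week for 4 sprays/application and 15.82 g/week for 8 sprays/application". It does not state applications per day or grams per spray.
- The displayed formula has 28 as its denominator and contains no expected weight.

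In the shells, footnote 3 of Table 14.1.4.1A divides net weight by "Expected net weight for 28 days of use", and footnote 3 of Listing 16.2.5.2 does likewise. Neither prints the weight. SAP section 5 lists no change in application frequency.

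**The concern.** A reference for compliant use should describe the scheduled use, and this one does not. If times means sprays, it is half the schedule. If times means applications, 4 or 8 a day also contradicts two a day. The sentence also disagrees with the gram figures in the same section.

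Bottle weight is the trial's quantitative measure of how much product was used, and the trial compares two spray regimens with placebo. Under-use is therefore a rival explanation for a null result or a flat dose response, and its reference needs to be unambiguous. A requirement of at least 50% of product also appears in the Per Protocol definition in Protocol 15.2 and in the SAP shells for Table 14.1.1 and Listing 16.2.1, although SAP 2.1 omits it. If that cut were applied by weight, it would depend on the same reference.

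**Working it through.** **Inputs.** Pumps per application (4 or 8) and two applications a day: SAP 1.2.1, Protocol 9.1 and 9.7. Expected use of 7.91 and 15.82 g/week: SAP 4.4.1. Bottle of 30 ml: Protocol 9.1. Kit of three bottles: Protocol 9.7 and 9.15. Bottle life: "Each bottle will be used for 10 days and brought to the weekly study appointment" (Protocol 9.15). SAP 4.4.1 speaks of four bottles, so both kit sizes are tried. The documents give neither weight per spray nor density. Weight per spray is derived below, and density is assumed to be about 1 g/ml.

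**1. Spray counts.** Sprays per day = pumps per application × applications per day: 4 × 2 = 8 and 8 × 2 = 16. Over 28 days that is 224 and 448. The SAP sentence gives 4 × 28 = 112 and 8 × 28 = 224, exactly half in each group.

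**2. The SAP's gram figures.** Their ratio reproduces the two regimens: 15.82/7.91 = 2.00. The value 7.91 itself cannot be reproduced without a weight per spray.

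**3. Implied weight per spray** = (g/week)/(7 × applications per day × sprays per application):

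- two applications a day: 7.91/(7 × 2 × 4) = 0.14125 g
- one application a day: 7.91/(7 × 1 × 4) = 0.2825 g

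**4. Which reading fits the supply?** The 8-pump regimen applied twice daily is 16 sprays a day, or 160 per 10-day bottle and 448 in 28 days.

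| Basis of g/week | 10 days (30 ml) | 28 days (90 ml, or 120 ml) |
|---|---|---|
| Two applications a day | 160 × 0.14125 = 22.6 g | 448 × 0.14125 = 63.28 g |
| One application a day | 160 × 0.2825 = 45.2 g | 448 × 0.2825 = 126.56 g |

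The first row fits. The second would need a density of at least 45.2/30 = 1.51 g/ml for the 10-day bottle, 126.56/90 = 1.41 g/ml for a three-bottle kit, or 126.56/120 = 1.05 g/ml for a four-bottle kit. The 4-pump regimen does not discriminate: even at 0.2825 g it uses 80 × 0.2825 = 22.6 g in 10 days.

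**5. Effect on the 28-day reference**, at 0.14125 g per spray:

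| | From g/week | From the sentence |
|---|---|---|
| 4 sprays per application | 7.91 × 4 = 31.64 g | 112 × 0.14125 = 15.82 g |
| 8 sprays per application | 15.82 × 4 = 63.28 g | 224 × 0.14125 = 31.64 g |
| Score with full use | 31.64/31.64 = 100% | 31.64/15.82 = 200% |
| Score with one application a day | 15.82/31.64 = 50% | 15.82/15.82 = 100% |
| Share of scheduled product that meets a 50% cut | 50% | 0.5 × 15.82/31.64 = 25% |

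The last three rows use the 4-spray group; the 8-spray group gives the same percentages.

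**6. The displayed formula.** As it appears, and ignoring sign, full use would give 31.64/28 × 100 = 113 and 63.28/28 × 100 = 226. Its left-hand side is missing from the extracted text, so part of the denominator may be lost too. These values are not used in the conclusion.

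**The case against.** A reader might infer that a subject taking half the doses will be reported as fully compliant. The documents do not support this. Reported percent compliance uses no daily spray count. SAP 4.4.1 defines it from net weight, supplies g/week figures stated per application regimen, and the shell footnotes divide by the expected weight for 28 days. Those grams fit the supply only as twice-daily amounts, so a half-dose subject would score about 50%. The right-hand column of the table in step 5 arises only if a programmer sets the stated grams aside and builds a weight from the sentence, using a weight per spray that the SAP does not give. The sentence also refers to compliance with the protocol, which is plainly twice daily.

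It would also be too strong to say that under-use would be hidden. Grams used in total and per day are tabulated whatever the reference, weights are listed by visit, missed doses are recorded, and skin swabs explore B244 presence or absence. The Per Protocol analysis is supportive, and no document ties the 50% cut to this sentence or says that it is applied by weight.

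All of this stands, and it limits the point to a minor one. It does not remove the contradiction. The sentence specifies a comparison for the cumulative and daily amounts, and it is the section's only description of compliant use as a daily spray count. The g/week figures do not state the applications per day behind them, and Listing 16.2.5.2 has an expected-weight column with no value given.

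**Conclusion.** The contradiction is certain. Read as sprays, the reference in SAP 4.4.1 is half the schedule in SAP 1.2.1 and Protocol 9.1 and 9.7, and it conflicts with the grams in its own section. The consequence is conditional. Built from the sentence, the expected weight would be halved and one application a day would read as 100%. Built as the second paragraph and the shells indicate, that subject scores about 50%.

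The supply argument assumes a density of about 1 g/ml, equal weight per pump, and the same 10-day bottle life and kit in both groups. With three bottles it holds for any density below about 1.4 g/ml; with four, the kit total alone excludes the one-application reading only below about 1.05 g/ml.

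This is a minor correction. It affects exposure and compliance reporting and any weight-based 50% Per Protocol cut, not the primary ITT analysis.

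**What to change.** - Reconcile the sentence in SAP 4.4.1 with the application schedule in SAP 1.2.1 and Protocol 9.1 and 9.7, stating sprays per application and applications per day separately.
- State the applications per day and the grams per spray behind 7.91 and 15.82 g/week.
- Give one 28-day expected weight per group. The SAP's own figures imply 31.64 g and 63.28 g.
- Make that weight the denominator of the displayed formula, as footnote 3 of Table 14.1.4.1A does. Check the formula in the source file first, since the extracted text may be incomplete.
- In the same edit, make the bottle count agree across SAP 4.4.1, the shells and the protocol.

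The cost is a few lines of SAP text. No new data are needed.
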